9.1.18 Status of Menstruation Recovery

If the first menstruation after the end of study drug administration is observed before the VISIT 7 in the Follow-up, the date of onset of the first menstruation is recorded in the eCRF. If menstruation recovery is not observed by the VISIT 7 in the Follow-up, follow-up will be continued as far as possible through telephone calls or other means until the recovery of the first menstruation. If menstruation recovery is observed during continued follow-up, the date of recovery should be recorded in the eCRF. The status at the end of menstruation follow-up will be recorded in the eCRF regarding menstruation recovery. After the Follow-up, follow-up will not be continued in subjects who undergo surgery or receive hormone therapy for the treatment of uterine fibroids before the recovery of menstruation.

9.2 Monitoring Subject Treatment Compliance

Subjects will be required to bring all remaining study medication and the blister card to each site visit. The investigator or subinvestigator records the start date and end date of administration in the eCRF during the Run-in period and Treatment period. Additionally, the dates of missed study medication administration during the Treatment period are recorded in the eCRF.

If a subject is persistently noncompliant with the study medication (TAK-385 40 mg tablet or TAK-385 placebo tablet) (eg, failure to take 10% or more of the scheduled doses after the last visit), it may be appropriate to withdraw the subject from the study. All subjects should be re instructed about the dosing requirement during study contacts. The authorized study personnel conducting the re-education must document the process in the subject source records.

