6.1.2 Dose Level and Regimen

At VISIT 3, subjects will be randomized in a 1:1 ratio to either the TAK-385 40 mg group or placebo group. Study drug (TAK-385 40 mg or TAK-385 placebo) will be administered from the day of VISIT 3 to the day before VISIT 6 (or until early termination) under double-blind conditions.

TAK-385 (or TAK-385 placebo) will be administered daily as a single oral dose before breakfast.

* In addition to Day -80~-26, informed consent may be obtained before Day -80.

**VISIT 2 and 3: On days 1 to 5 of the menstrual cycle

Figure 6.a Schematic of Study Design

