3. Protocol deviation. The discovery after randomization that the subject failed to meet protocol entry criteria or did not adhere to protocol requirements, and continued participation poses an unacceptable risk to the subject's health.
4. Lost to follow-up. The subject did not return to the clinic and attempts to contact the subject were unsuccessful. Attempts to contact the subject must be documented.
5. Withdrawal by subject. The subject wishes to withdraw from the study. The reason for withdrawal, if provided, should be recorded in the eCRF.

Note: All attempts should be made to determine the underlying reason for the withdrawal and, where possible, the primary underlying reason should be recorded (withdrawal due to an AE or lack of efficacy should not be recorded in the "Withdrawal by subject" category).

6. Study terminated by sponsor. The sponsor terminates the study.
7. Pregnancy. The subject is found to be pregnant.

Note: If the subject is found to be pregnant, the subject must be withdrawn immediately. The procedure is described in Section [9.1.10](#).

8. Lack of efficacy. The investigator or subinvestigator judges TAK-385 shows no efficacy based on the menstrual blood loss, menstrual status, and use of analgesics (eg, a notable increase in the frequency of taking analgesics due to intolerable pain after start of study drug administration) and judges continued participation in the study would pose an unacceptable risk to the subject.
9. Other.

Note: The specific reasons should be recorded in the "specify" field of the eCRF.

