7.6 Procedures for Discontinuation or Withdrawal of a Subject

The investigator or subinvestigator may discontinue a subject's study participation at any time during the study when the subject meets the study termination criteria described in Section [7.5](#). In addition, a subject may discontinue her participation without giving a reason at any time

during the study. Should a subject's participation be discontinued, the primary criterion for termination must be recorded by the investigator or subinvestigator. In addition, efforts should be made to perform all procedures scheduled for the Early Termination Visit. Discontinued or withdrawn subjects will not be replaced.

CONFIDENTIAL

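### Section 9.2 suggests withdrawal for missed doses without a health risk; this is inconsistent with Sections 7.5 and 7.6 and can move a subject's primary 28-day window earlier

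*Protocol*

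**What the plan says.** Protocol Section 9.2 opens its rule with "If a subject is persistently noncompliant with the study medication", gives as its example "failure to take 10% or more of the scheduled doses after the last visit", and concludes that "it may be appropriate to withdraw the subject from the study". It does not define persistence and attaches no safety condition. It also requires a milder response: "All subjects should be re instructed about the dosing requirement during study contacts", with the re-education documented.

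Section 7.5 lists the reasons for discontinuation. Item 3 covers a subject who "did not adhere to protocol requirements, and continued participation poses an unacceptable risk" to her health. Item 9 (Other) is open, and its note says "The specific reasons should be recorded in the" specify field. Section 7.6 lets the investigator discontinue a subject who meets the Section 7.5 criteria and adds that "Discontinued or withdrawn subjects will not be replaced".

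Under Section 6.1.2, double-blind drug is given from VISIT 3 "to the day before VISIT 6 (or until early termination) under double-blind conditions". Section 9.1.17 ends the diary at the same point. SAP Section 7.1.1 takes the primary window as the date of the last dose plus the 27 preceding days, and counts subjects with available data. SAP Section 7.1.4 plans no imputation unless otherwise specified. Protocol Section 13.1.1 puts every randomised subject who was dosed at least once in the FAS.

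**The concern.** Sites are given two thresholds for the same behaviour. Section 7.5 item 3 asks for a health risk and Section 9.2 does not. The difference matters because the primary endpoint is the maximum NRS over the 28 days ending at the last dose. Withdrawal does not simply leave that value missing: it selects a different, earlier 28 days. The later diary days are never collected, and the subject stays in the FAS as the protocol defines it.

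A discretionary site decision taken after randomisation can therefore determine which data decide a subject's primary outcome. Protocol Section 6.2.1 justifies the treatment length by saying that about three months are needed to assess pain, so an earlier window is not the assessment the design intended.

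**Working it through.** **1. Trigger.** VISIT 3 is Day 1 and VISIT 4 is Day 29, so 28 doses fall between them. 10% × 28 = 2.8, so 3 missed tablets meet the example (25/28 = 89.3% taken).

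**2. Window.** Window = [final dose day − 27, final dose day]. VISITS 4, 5 and 6 are Days 29, 57 and 85 (Protocol Section 9.3). The final dose is taken to be on the day before the visit.

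| Dosing ends at | Final dose | Primary window | Shift |
|---|---|---|---|
| VISIT 6 (completer) | Day 84 | Days 57-84 | none |
| VISIT 5 | Day 56 | Days 29-56 | 28 days earlier |
| VISIT 4 | Day 28 | Days 1-28 | 56 days earlier |

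If that day's tablet was taken before VISIT 4 or 5, the window is one day later. If the last tablets were skipped, it is earlier still. VISIT 4 is the first on-treatment compliance check, so the Days 1-28 case needs one visit interval to count as persistent. If persistence needs more than one interval, VISIT 5 is the earliest scheduled visit at which it could apply.

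**3. Can another analysis recover Days 57-84?** The time-course summary (SAP Sections 7.1.1 and 7.8.2.2) is cut at Follow-up Day 3. After a final dose on Day 56 the cut is Day 59, which leaves at most Days 57-59, or 3 of 28 days. After a final dose on Day 28 the cut is Day 31, which leaves none. The Handling Rules for Analysis Data were not among the documents. They could reclassify the subject but could not supply diary days that were never recorded.

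**4. What the earlier windows contain.**
- *VISIT 5 case.* The phase 2 pain result in Protocol Section 4.2 is for Weeks 6 to 12. On this SAP's scale (Week w = Day 7w + 1, assumed to apply to phase 2), Week 6 is Day 43. Days 29-42, 14 of the 28 window days, fall before it.
- *VISIT 4 case.* VISIT 3 falls on menstrual day d = 1 to 5, and Section 6.2.1 says that pain occurs mostly during menstruation. Bleeding days left from Day 1 = max(0, L − d + 1), where L is the length of bleeding. For L = 3, the minimum required at entry, this gives 3, 2, 1, 0, 0. For L = 7 (assumed) it gives 7, 6, 5, 4, 3.

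**5. Power, as illustration only.** Power = Σ P(X = x) P(Y = y) over all tables with two-sided Fisher p ≤ 0.05, by full binomial enumeration. The plan's figure reproduces: 28 per arm at 65% vs 20% gives 90.4% (stated as above 90%). All 32 per arm give 95.1%. Next, assume that k subjects are certain non-responders. Neither k nor their response rate is in the documents.

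| 32 per arm | k = 1 | k = 2 | k = 3 |
|---|---|---|---|
| Active arm only | 93.2% | 90.8% | 87.7% |
| k in each arm | 94.0% | 92.8% | 91.4% |
| Placebo arm only | 95.7% | 96.3% | 96.8% |

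One of the nine cases is below 90%. At the phase 2 rates (22/29 vs 5/34) with 32 per arm, three certain non-responders in the active arm leave 99.7%. If the affected subjects respond at the planned rate, power does not change.

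**The case against.** The strongest reply is that Section 9.2 confers no power of its own. Section 7.6 ties investigator discontinuation to Section 7.5, where non-adherence needs a health risk. The Section 9.2 sentence is permissive, its threshold is only an example, and re-instruction is required in any case. This largely stands. A reader might infer that Section 9.2 freely authorises withdrawal for three missed tablets, but the documents do not go that far. What they leave is a suggestion with no condition, and an open category that can hold it.

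The second reply is that the shift comes from the final-dose anchor and from stopping the diary at early termination, so it affects every discontinuation. This is also true. Section 9.2 is one cause among several. It differs from safety withdrawal or the subject's own choice in being started by the site and avoidable.

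The third reply is that no harm is shown. The Weeks 6 to 12 result tells us when phase 2 pain was summarised and not that the effect is absent earlier. Protocol Section 4.1 expects faster onset than with GnRH agonists, which it says take about 3 to 4 weeks, so Days 29-56 may already show the effect. This stands too. A reader might infer bias against TAK-385 or an underpowered trial. The Days 1-28 window could lean towards non-response because of the entry menstruation, but little or no bleeding may remain. The documents do not give the number of such subjects, their split between arms or their response rate.

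**Conclusion.** The inconsistency and the window shift are real, and the severity is minor. Section 9.2 suggests withdrawal for missed doses without the health-risk condition in Section 7.5 item 3, and given Section 7.6 a withdrawal on that basis can be recorded only under item 9. If it happens, the subject's primary window moves about 28 days earlier (VISIT 5) or, if one interval counts as persistent, about 56 days earlier (VISIT 4), and the planned Days 57-84 data are lost almost entirely.

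This rests on a final dose the day before the visit, on the diary stopping at early termination as written, and on the FAS as the protocol defines it. The unseen Handling Rules might change how she is classified. The frequency, the direction of any bias and any loss of power are unknown, so the power table is not evidence that the trial is at risk.

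**What to change.** In Protocol Section 9.2, delete the withdrawal option and keep the re-instruction and its documentation. State there and in Section 7.5, including under item 9, that missed doses alone, without a health risk, are not a reason for the site to end participation. Diary and visits should continue to VISIT 6 as far as the subject is willing. SAP Section 7.7 already summarises compliance below 80% and from 80% to below 90%, so poor adherence remains visible.

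The cost is protocol wording in two sections. The downside is that some poorly adherent subjects remain on study and in the FAS. Withdrawal for safety or at the subject's own wish is unaffected.

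A reader might infer that this restores the Days 57-84 window for every poor adherer. It does not: a subject who stops taking tablets still has an early final dose, and the SAP still anchors her window on it. How such subjects are scored needs a separate decision. The change removes one avoidable, site-initiated cause of lost primary data and does no more than that.

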9.3 Schedule of Observations and Procedures

The schedule for all study-related procedures for all evaluations is shown in [Appendix A](#). Assessments should be completed at the designated visit/time points.

9.3.1 Screening and Run-in

9.3.1.1 *VISIT 1 (Day -80 through Day -26)*

Subjects undergo examinations and tests for eligibility assessment at VISIT 1 (between 80 and 26 days prior to the initial dose of the study drug for the Treatment). Subject eligibility is determined based on the inclusion and exclusion criteria as described in Section [7.0](#). See Section [9.1.14](#) for procedures for documenting the records of subjects withdrawn before study drug administration in the Screening and Run-in. Study drugs for the Run-in are started in single-blind conditions from the day of first menstruation after VISIT 1.

The following procedures should be performed at VISIT 1:

- Informed consent
- Inclusion and exclusion criteria
- Pap smear test (if a subject has no test result obtained within 1 year before VISIT 1, perform pap smear test between VISIT 1 and VISIT 2)
- Demographics and concurrent medical conditions
- Medical history and medication history
- Pregnancy test (urine)
- Physical examination
- Vital signs, height and weight
- Patient diary (distributed)
- Transvaginal ultrasound (see Section [9.1.16](#). If it cannot be performed at VISIT 1, it may be delayed up to the day before VISIT 2 [but should be done as early as possible])
- Clinical laboratory tests
- Standard 12-lead ECG
- AE
- Concomitant medications
- Dispensing of study drugs for the Run-in

9.3.1.2 *VISIT 2 (Day -42 through Day -21)*

The subject visits the study site between the first and fifth day of their first menstruation after VISIT 1, without taking the study drug for the Run-in in the morning. The subject should be

CONFIDENTIAL

screened in accordance with the inclusion and exclusion criteria as described in Section 7.0, including confirmation of the description in the patient diary. See Section 9.1.14 for procedures for documenting the records of subjects withdrawn in the Screening and Run-in.

The following procedures should be performed at VISIT 2:

- Inclusion and exclusion criteria
- Pap smear test (if a subject has no test result obtained within 1 year before VISIT 1, perform pap smear test between VISIT 1 and VISIT 2)
- Pregnancy test (urine)
- Physical examination
- Vital signs and weight
- Patient diary (collected and distributed)
- Clinical laboratory tests
- AE
- Concomitant medications

9.3.2 Treatment

9.3.2.1 VISIT 3 (Day 1)

The subject visits the study site between the first and fifth day of the second menstruation after VISIT 1, without taking the study drug for the Run-in in the morning.

Subjects who satisfy all of the inclusion criteria and do not meet the exclusion criteria are randomized in the manner described in Section 8.2. Study drugs for the Treatment are started on the day of VISIT 3. If a dose is missed before breakfast, subjects may take the TAK-385 tablet before lunch on the same day. If a dose is missed before breakfast and lunch, subjects may take the TAK-385 tablet before dinner on the same day. The procedure for documenting the records of subjects withdrawn before randomization is provided in Section 9.1.14. Subjects are randomized after eligibility assessment on Day 1 (VISIT 3).

The following procedures should be performed at VISIT 3:

- Inclusion and exclusion criteria
- Pregnancy test (urine)
- Physical examination
- Vital signs and weight
- Patient diary (collected and distributed)
- Transvaginal ultrasound (see Section 9.1.16. If it cannot be performed at VISIT 3, it is performed between VISIT 2 and VISIT 3 [but should be done at nearest point to VISIT 3])

- UFS-QOL
- Clinical laboratory tests
- Pharmacodynamic measurements
- Standard 12-lead ECG
- AE
- Concomitant medications
- Dispensing of study drugs for the Treatment
- Compliance of study drug administration
- PGx sample collection (perform only in subjects who consent to participate in PGx research [see Section 9.1.12])

9.3.2.2 VISIT 4 (Day 29)

The following procedures should be performed at VISIT 4:

- Pregnancy test (urine)
- Physical examination
- Vital signs and weight
- Patient diary (collected and distributed)
- Clinical laboratory tests
- Pharmacodynamic measurements
- AE
- Concomitant medications
- Dispensing of study drugs for the Treatment
- Compliance of study drug administration
- PGx sample collection (perform only in subjects who consent and from whom the sample has not been collected [see Section 9.1.12])

9.3.2.3 VISIT 5 (Day 57)

The following procedures should be performed at VISIT 5:

- Pregnancy test (urine)
- Physical examination
- Vital signs and weight
- Patient diary (collected and distributed)

CONFIDENTIAL

- Clinical laboratory tests
- Pharmacodynamic measurements
- AE
- Concomitant medications
- Dispensing of study drugs for the Treatment
- Compliance of study drug administration
- PGx sample collection (perform only in subjects who consent and from whom the sample has not been collected [see Section 9.1.12])

9.3.3 Final Visit or Early Termination

9.3.3.1 VISIT 6 (Day 85) (or Early Termination)

The final visit during the treatment will be performed on VISIT 6 (85 days after the initial dose of the study medication for the Treatment). The following procedures should be performed. If early termination occurs during the Treatment, the same procedures scheduled at VISIT 6 should be performed.

- Pregnancy test (urine)
- Physical examination
- Vital signs and weight
- Patient diary (collected)
- Transvaginal ultrasound (see Section 9.1.16)
- UFS-QOL
- Clinical laboratory tests
- Pharmacodynamic measurements
- Standard 12-lead ECG
- AE
- Concomitant medications
- Compliance of study drug administration
- PGx sample collection (perform only in subjects who consent and from whom the sample has not been collected [see Section 9.1.12])

For all subjects receiving study medication, the investigator or subinvestigator must complete the Subject Status eCRF page.

9.3.4 Follow-up

9.3.4.1 VISIT 7 (*Final visit of the Follow-up, 28 days after last dose*)

The Follow-up lasts for 4 weeks (28 days) from the day after the final dose of study drug. The following procedures should be performed at the final visit of the Follow-up (VISIT 7). If early termination occurs during the Treatment, the same procedures scheduled at VISIT 7 should be performed 4 weeks (28 days) after the end of treatment. If study termination occurs during the Follow-up, the same procedures scheduled at VISIT 7 should be performed.

- Pregnancy test (urine)
- Physical examination
- Vital signs and weight
- Status of menstruation recovery
- Clinical laboratory tests
- Pharmacodynamic measurements
- Standard 12-lead ECG
- AE
- Concomitant medications
- PGx sample collection (perform only in subjects who consent and from whom the sample has not been collected [see Section 9.1.12])

9.3.5 Post Study Care

The study medication will not be available upon completion of the subject's participation in the study. The subject should be returned to the care of a physician and standard therapies as required.

If the recovery of the first post-treatment menstruation is not observed by the visit at the end of the Follow-up (VISIT 7), the subject will undergo further follow-up using possible means such as by telephone interview, until the recovery of the first post-treatment menstruation is observed.

9.4 Biological Sample Retention and Destruction

Samples of 5 mL whole blood collected for PGx will be stored frozen at [REDACTED]
[REDACTED] (See the attachment 1).

The collected samples will be retained at specimen storage agency up to 15 years after the completion of the study.

When subjects request disposal of a stored sample during the retention period or the sponsor discontinues the application aimed at obtaining approval from the Ministry of Health, Labour and Welfare, the site will ask [REDACTED] to destroy the sample via the sponsor according to the procedure. The [REDACTED] will destroy the sample in

CONFIDENTIAL

accordance with the procedure, and notify the site and sponsor. However, any samples should not be destroyed if all the documents (including medical records) have been destroyed which could identify the subject and it is impossible to link the sample to the subject.

Even if the sample can be linked to the subject, when PGx investigation has been conducted, the remaining samples will be destroyed and the results of PGx investigation of anonymized subject will be retained by the sponsor.

The sponsor will build a management system required for protection of the subject's personal information, define standards for collecting store and destruction of samples, and prepare appropriate procedures.

10.0 ADVERSE EVENTS

10.1 Definitions

10.1.1 AEs

An AE is defined as any untoward medical occurrence in a clinical investigation subject who has signed informed consent to participate in a study; it does not necessarily have to have a causal relationship with this treatment or study participation.

An AE can therefore be any unfavorable and unintended sign (eg, a clinically significant abnormal laboratory finding), symptom, or disease temporally associated with the study participation whether or not it is considered related to the drug or study procedures.

10.1.2 Additional Points to Consider for AEs

An untoward finding generally may:

- Indicate a new diagnosis or unexpected worsening of a pre-existing condition. (Intermittent events for pre-existing conditions or underlying disease should not be considered AEs.)
- Necessitate therapeutic intervention.
- Require an invasive diagnostic procedure.
- Require discontinuation or a change in dose of study medication or a concomitant medication.
- Be considered unfavorable by the investigator or subinvestigator for any reason.
- AEs caused by a study procedure (eg, a bruise after blood draw) should be recorded as an AE.

Diagnoses vs signs and symptoms:

- Each event should be recorded to represent a single diagnosis. Accompanying signs (including abnormal laboratory values or ECG findings) or symptoms should NOT be recorded as additional AEs. If a diagnosis is unknown, sign(s) or symptom(s) should be recorded appropriately as an AE(s).

Laboratory values and ECG findings:

- Changes in laboratory values or ECG parameters are only considered to be AEs if they are judged to be clinically significant (ie, if some action or intervention is required or if the investigator or subinvestigator judges the change to be beyond the range of normal physiologic fluctuation) by the investigator or subinvestigator. A laboratory re-test and/or continued monitoring of an abnormal value are not considered an intervention. In addition, repeated or additional noninvasive testing for verification, evaluation or monitoring of an abnormality is not considered an intervention.
- If abnormal laboratory values or ECG findings are the result of pathology for which there is an overall diagnosis (eg, increased creatinine in renal failure), the diagnosis only should be reported appropriately as an AE.

CONFIDENTIAL

Pre-existing conditions:

- Pre-existing conditions (present at the time of signing of informed consent) are considered concurrent medical conditions and should NOT be recorded as AEs. Baseline evaluations (eg, laboratory tests, ECG, X-rays etc.) should NOT be recorded as AEs unless related to study procedures. However, if the subject experiences a worsening or complication of such a concurrent condition after informed consent is signed, the worsening or complication should be recorded appropriately as an AE. Investigator or subinvestigator should ensure that the event term recorded captures the change in the condition (eg, “worsening of...”).
- If a subject has a pre-existing episodic condition (eg, asthma, epilepsy) any occurrence of an episode should only be captured as an AE if the episodes become more frequent, serious or severe in nature, that is, investigator or subinvestigator should ensure that the AE term recorded captures the change in the condition from Baseline (eg, “worsening of...”).
- If a subject has a degenerative concurrent condition (eg, cataracts, rheumatoid arthritis), worsening of the condition should only be captured as an AE if occurring to a greater extent to that which would be expected. Again, investigator or subinvestigator should ensure that the AE term recorded captures the change in the condition (eg, “worsening of...”).

Worsening of AEs:

- If the subject experiences a worsening or complication of an AE after starting administration of the study medication, the worsening or complication should be recorded appropriately as a new AE. Investigator or subinvestigator should ensure that the AE term recorded captures the change in the condition (eg, “worsening of...”).
- If the subject experiences a worsening or complication of an AE after any change in study medication, the worsening or complication should be recorded as a new AE. Investigator or subinvestigator should ensure that the AE term recorded captures the change in the condition (eg, “worsening of...”).

Changes in severity of AEs:

- If the subject experiences changes in severity of an AE that are not related to starting or changing the study medication, the event should be captured once with the maximum severity recorded.

Preplanned surgeries or procedures:

- Preplanned procedures (surgeries or therapies) that were scheduled prior to signing of informed consent are not considered AEs. However, if a preplanned procedure is performed early (eg, as an emergency) due to a worsening of the pre-existing condition, the worsening of the condition should be captured appropriately as an AE. Complications resulting from any planned surgery should be reported as AEs.

Elective surgeries or procedures:

- Elective procedures performed where there is no change in the subject's medical condition should not be recorded as AEs, but should be documented in the subject's source documents. Complications resulting from an elective surgery should be reported as AEs.

Insufficient clinical response (lack of efficacy):

- Insufficient clinical response, efficacy, or pharmacologic action, should NOT be recorded as an AE. The investigator or subinvestigator must make the distinction between exacerbation of pre-existing illness and lack of therapeutic efficacy.

Overdose:

- Cases of overdose with any medication without manifested side effects are NOT considered AEs, but instead will be documented on an Overdose page of the eCRF. Any manifested side effects will be considered AEs and will be recorded on the AE page of the eCRF.

Worsening of the target disease:

- Worsening of expected conditions (measured by the primary efficacy and other endpoints) within the normal course will not be recorded as AEs.

